- Unwilling to abstain during the study from using smoking cessation aids other than those provided by the study;
- Experienced a prior adverse drug reaction to varenicline;
- Report an unstable medical condition, epilepsy, or severe renal impairment;
- Had an inpatient psychiatric hospitalization and/or serious suicidal ideation or suicide attempt in the prior six months;
- Have active problem substance use (other than nicotine) severe enough to compromise ability to safely participate in the study protocol.
- Evidence of active problem substance use severe enough to compromise ability to safely participate, in the investigator's opinion;

- Unwilling to provide urine samples;
- Any condition or situation that would, in the investigator's opinion, make it unlikely that the participant could adhere safely to the study protocol;
- Ward of the state.

Randomization

Eligible participants will be randomly assigned in a 1:1:1 ratio, in blocks of 6, to V+BC (varenicline and behavioral counseling), P+BC (identical appearing placebo and behavioral counseling), or EUC (enhanced usual care). Randomization will be stratified by secondary or post-secondary school status. The randomization scheme will be computer generated by the Massachusetts General Hospital (MGH) Research Pharmacy by personnel with no other interactions with study staff or participants. Randomization codes will be held in the research pharmacy and made available to study investigators only in the case of urgent medical need. There will be separate randomization codes for apo-varenicline, imported from Canada under a provisional FDA allowance, and domestic generic varenicline will full FDA approval. Treatment will be assigned according to study number, assigned sequentially to eligible participants who enroll in the trial and attend the baseline visit.

Masking/Blinding

Outcome assessors, data managers, and analysts will be blinded to treatment assignments. All study staff and participants will be blind to study medication assignment for the primary outcome comparing V+BC and P+BC. Interventionists and their clinical supervisors will be unblinded to assignment to behavioral counseling and will not be involved in assessments, data management, or data analysis.

Analytic Approach

Primary Outcome

The primary outcome for the study will be...

1. Cotinine-verified self-reported nicotine vaping abstinence from week 9 to week 12 of the study.

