1. Cotinine-verified self-reported nicotine vaping abstinence from week 9 to week 24 of the study.
 - a. [Time frame] Using self-reported abstinence (see primary outcome) and biochemical verification based on urine/saliva samples (see primary outcome) collected during weeks 9, 10, 11, 12, 16, 20, and 24, the secondary outcome will consist of continuous abstinence for each participant converted to a binary value (1 = abstinent across all 7 study visits, 0 = non-abstinent for at least one of the 7 study visits).
2. Cotinine-verified self-reported nicotine vaping abstinence at week 12 of the study.
 - a. [Time frame] Using self-reported abstinence (see primary outcome) and biochemical verification based on urine/saliva samples (see primary outcome) collected during week 12, the secondary outcome will consist of 7-day point-prevalence abstinence for each participant converted to a binary value (1 = abstinent over 7 days ending at week 12, 0 = otherwise).
3. Summed scores on the Minnesota Nicotine Withdrawal Scale (MNWS; Cappelleri, Bushmakin, Baker, Merikle, Olufade, & Gilbert, 2005), a 9-item inventory with scores ranging from 0 to 36 (higher scores indicate greater severity of nicotine withdrawal).
 - a. [Time frame] The inventory will be administered at baseline, every week from weeks 1 – 12, and weeks 16, 20, and 24.
4. Summed scores on the Questionnaire of Vaping Craving (QVC; Dowd, Motschman, & Tiffany, 2019), a 10-item inventory with scores ranging from 10 to 70 (higher scores indicate greater cravings to vape).
 - a. [Time frame] The inventory will be administered at baseline, every week from weeks 1 – 12, and weeks 16, 20, and 24.
5. Summed scores on the General Distress subscale of the Mood and Anxiety Symptoms Questionnaire (MASQ-D30; Lin, Yung, Wigman, Killackey, Baksheev, & Wardenaar, 2014).
 - a. [Time frame] The inventory will be administered at enrollment, baseline and monthly during weeks 4, 8, 12, 16, 20, and 24.
6. Number of participants who report one or more adverse events as measured by the Neuropsychiatric Adverse Events Interview (NAEI; Anthenelli et al., 2016).

- a. [Time frame] The interview will be conducted at enrollment, baseline, and monthly during weeks 4, 8, 12, 16, 20, and 24.

Missing Data

Missing outcome data for the 2 vaping abstinence outcomes and the 3 inventory measures will be multiply imputed.

Biochemically-Verified Vaping Abstinence

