2. We will assess a pair of dummy-coded contrasts comparing the EUC group (coded as 0) against (1) the V+BC group (coded as 1) and (2) the P+BC group (coded as 1). Statistical significance will be determined via an analysis of variance comparing a simpler null model (with contrasts for V+BC and P+BC fixed to zero) against the more complex model with both contrasts freely estimated. If the Wald test for the model comparison is significant, we will conduct post-hoc tests assessing the 3 possible comparisons between groups (EUC vs. P+BC, EUC vs. V+BC, and P+BC vs. V+BC). We will conduct this analysis for our primary vaping abstinence outcome as well as our two secondary vaping abstinence outcomes.

Table 1 summarizes all secondary analyses for the vaping abstinence outcomes. Tests will be deemed statistically significant for $p < 0.05$ following a correction using the Benjamini-Hochberg method across the 5 analyses.

Table 1: Secondary analyses for vaping abstinence outcomes

Vaping abstinence outcome	Contrast
Continuous abstinence (over weeks 9 – 12)	Omnibus test for EUC vs. V+BC, EUC vs. P+BC, and P+BC vs. V+BC
Continuous abstinence (over weeks 9 – 24)	Contrast of P+BC vs. V+BC (No EUC)
Point-prevalence abstinence (week 12)	Omnibus test for EUC vs. V+BC, EUC vs. P+BC, and P+BC vs. V+BC

Inventory Measures

We will use a linear regression model to assess the post-baseline summed scores collected over weeks 1 – 12 (at weekly or monthly intervals) for (1) the MNWS, (2) the QVC, and (3) the MASQ-D30. The linear model will be estimated using generalized estimating equations (GEE; Liang & Zeger, 1986),

providing estimates and standard errors robust to violations of distributional assumptions (e.g., normality) and heteroscedasticity.

The linear regression model will include covariates for (a) biological sex and baseline summed scores for the ECDI (see above), (b) a participant's baseline score on the given inventory measure, and (c) linear and quadratic time trend terms using number of days since the baseline visit. Covariates will be standardized (mean-centered and scaled by the standard deviation). The analysis will be intent-to-treat; all subjects randomized at the beginning of the study will be included in the analysis, irrespective of whether they receive their assigned behavioral treatment or take their assigned medication.

We will conduct two types of analyses:

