3. We will assess a single dummy-coded contrast comparing the P+BC group (coded as 0) to the V+BC group (coded as 1), excluding participants in the EUC group. Statistical significance will be determined using a z-test applied to the pooled mean estimate divided by the pooled standard error. This will be a secondary analysis.
4. We will assess a pair of dummy-coded contrasts comparing the EUC group (coded as 0) against (1) the V+BC group (coded as 1) and (2) the P+BC group (coded as 1). Statistical significance will be determined via an analysis of variance comparing a simpler null model (with contrasts for V+BC and P+BC fixed to zero) against the more complex model with both contrasts freely estimated. If the Wald test for the model comparison is significant, we will conduct post-hoc tests assessing the 3 possible comparisons between groups (EUC vs. P+BC, EUC vs. V+BC, and P+BC vs. V+BC). This will be an exploratory analysis.

Table 2 summarizes all secondary and exploratory analyses for the inventory measures. Tests will be deemed statistically significant for $p < 0.05$ following a correction using the Benjamini-Hochberg method across the 3 secondary analyses and 3 exploratory analyses, respectively.

Table 2: Secondary and exploratory analyses for inventory measures

Inventory measure	Contrast	Exploratory
MNWS	Contrast of P+BC vs. V+BC (No EUC)	Yes
	Omnibus test for EUC vs. V+BC, EUC vs. P+BC, and P+BC vs. V+BC	
QVC	Contrast of P+BC vs. V+BC (No EUC)	Yes
	Omnibus test for EUC vs. V+BC, EUC vs. P+BC, and P+BC vs. V+BC	
MASQ-D30	Contrast of P+BC vs. V+BC (No EUC)	Yes
	Omnibus test for EUC vs. V+BC, EUC vs. P+BC, and P+BC vs. V+BC	

Adverse events

We will tally the number participants who report one or more adverse events during the NAEI interview across weeks 4, 8, and 12, looking specifically at the 2 x 2 contingency tables for (a) the P+BC group versus V+BC group, and (b) the EUC group versus the V+BC group. We will then assess whether the number of participants reporting one or more adverse events differs between the two groups using Fisher's exact test. Differences between groups will be deemed statistically significant for $p < 0.025$.

Sensitivity Analyses

Across our primary and secondary analyses, at a minimum we will conduct the following sensitivity analyses:

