1. We will test whether our conclusion on efficacy is robust to the inclusion/exclusion of the two covariates (biological sex and nicotine dependence severity). We will rerun analyses excluding these covariates and see if conclusions change.
2. We will test whether our conclusion on efficacy is robust to the approach for imputation of missing data. We will (a) rerun the adjusted (i.e., with covariates) models on the observed data only and (b) rerun the adjusted models on a dataset with the observed data and all missing outcome data imputed as non-abstinent.
3. We will conduct a per protocol analysis by evaluating results among participants who use varenicline on most days in the trial (e.g., > 50 or 75%).

Power

Sample size was determined based on the assumption that use of varenicline for vaping cessation in adolescents would require an effect that at least doubled cessation rates over placebo to be worth the risks inherent in use of pharmacotherapy. Abstinence rates of 24% have been reported with TIQ alone in adolescents who vaped and were not necessarily dependent (Graham, Jacobs, & Amato, 2020; Graham, Amato, Cha, Jacobs, Bottcher, & Papandonatos, 2021). In this trial, requiring nicotine dependence to enroll, we postulate that addition of varenicline to behavioral counseling and TIQ will double abstinence rates. A sample size of 100 per arm, with 80 analyzable per arm, would yield power of 0.88 with a two-sided alpha of 0.05 with abstinence rates of 25% in the P+BC arm and 50% in the V+BC arm.

Software and Data Management

All analyses will be done using the statistical software R (version 4.1.1; R Core Team, 2021) and integrated development environment RStudio (version 2020.9.0.351; RStudio Team, 2021). Data will be prepared using the R packages ‘dplyr’ (version 1.0.7; Wickham, François, Henry, & Müller, 2021) and ‘tidyr’ (version 1.1.4; Wickham, 2021). Models will be fit using the R package ‘geepack’ (version 1.3-2; Højsgaard, Halekoh, & Yan, 2006). Missing data will be imputed using the R package ‘mice’ (version 3.13.0; Van Buuren & Groothuis-Oudshoorn, 2011). Reproducible code and de-identified data will be organized using the R package ‘targets’ (version 0.8.1; Landau, 2021).

References

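### The adverse-event comparison ignores the baseline NAEI already collected: the Fisher test is valid, but it gives up power if pre-treatment symptoms recur on treatment

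*SAP*

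**What the plan says.** Under Secondary Outcomes, item 6, the SAP sets the NAEI schedule: "The interview will be conducted at enrollment, baseline, and monthly during weeks 4, 8, 12, 16, 20, and 24". So two interviews take place before treatment.

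Under Adverse events, only the on-treatment interviews are used: "We will tally the number participants who report one or more adverse events during the NAEI interview across weeks 4, 8, and 12". The counts go into "2 x 2 contingency tables for (a) the P+BC group versus V+BC group, and (b) the EUC group versus the V+BC group". The SAP then states: "We will then assess whether the number of participants reporting one or more adverse events differs between the two groups using" Fisher's exact test, with significance at p < 0.025. No stratification, covariate or new-onset condition is stated.

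Two other sections bear on this:

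- Statistical Models and Tests, Inventory Measures: the models for the MNWS, QVC and MASQ-D30 each include the participant's "baseline score on the given inventory measure".
- Sensitivity Analyses: the covariate check reads "We will test whether our conclusion on efficacy is robust to the inclusion/exclusion of the two covariates", and the imputation check is framed in the same terms. Neither brings the baseline NAEI into the adverse-event comparison. The per-protocol item selects on medication use and does not do so either.

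**The concern.** The outcome is a yes/no count of any event over three interviews. If someone who had symptoms before the first tablet reports them again at week 4, that person counts as an event in either arm. Randomization balances such people in expectation, so there is no bias under the null. They do add background events that carry little information about varenicline, and this shrinks the visible difference between arms.

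The SAP accepts the principle of using a baseline value for its three symptom scores. It does not apply it to its only between-arm test of adverse events. (MASQ-D30 distress is also compared between arms, but as a symptom score.) The Power section justifies the target effect by weighing benefit against the risks of drug treatment. In a safety comparison, low power favours a report of no difference, so lost power works against detecting a real excess on varenicline.

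**Working it through.** **The plan's own figure.** The SAP gives no power for adverse events. Its one power figure is for the primary efficacy contrast: 80 analyzable per arm, 25% vs 50%, two-sided 0.05, power 0.88. Exact enumeration of Fisher's test gives 0.883 and a continuity-corrected z-test gives 0.882, so it reproduces.

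**Inputs from the SAP.** 100 randomized and 80 analyzable per arm; alpha 0.025 per contrast; outcome is any NAEI event at weeks 4, 8 or 12.

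**Inputs assumed, because the SAP gives none.** Conditional odds ratio 2.5 for varenicline; baseline prevalence of 10–40%; control-arm event rates by baseline status as tabulated.

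**Mechanism, one setting worked through.** Take prevalence 30%, with control event rates of 70% if symptomatic at baseline and 20% if not.

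- Varenicline rate, symptomatic: odds 0.70/0.30 × 2.5 = 5.83, so 5.83/6.83 = 0.854.
- Varenicline rate, not symptomatic: odds 0.20/0.80 × 2.5 = 0.625, so 0.625/1.625 = 0.385.
- Overall control rate: 0.3 × 0.70 + 0.7 × 0.20 = 0.350.
- Overall varenicline rate: 0.3 × 0.854 + 0.7 × 0.385 = 0.525.
- Odds ratio seen by the unadjusted table: (0.525/0.475) / (0.350/0.650) = 2.05, against 2.5 within each stratum.

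Exact enumeration of Fisher's test for 0.350 vs 0.525 with 80 per arm gives power 0.43, in line with the simulated value below.

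**Simulation.** 10,000 trials per setting, alpha 0.025, Monte Carlo standard error about 0.005. Each cell shows 80 per arm, then 90 per arm. CMH is the Cochran-Mantel-Haenszel test stratified by baseline NAEI status.

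| Baseline prevalence; control event rate if positive / negative at baseline | Fisher | Unadjusted chi-square | Exact stratified | CMH |
|---|---|---|---|---|
| 30%; 70/20 | 0.437, 0.510 | 0.497, 0.564 | 0.578, 0.631 | 0.609, 0.663 |
| 40%; 75/25 | 0.428, 0.512 | 0.490, 0.558 | 0.573, 0.628 | 0.610, 0.658 |
| 20%; 60/20 | 0.523, 0.582 | 0.583, 0.637 | 0.599, 0.656 | 0.632, 0.690 |
| 30%; 35/20 | 0.587, 0.658 | 0.646, 0.710 | 0.623, 0.693 | 0.656, 0.725 |
| 10%; 30/10 | 0.371, 0.422 | 0.446, 0.487 | 0.408, 0.465 | 0.449, 0.507 |
| 10%; 20/5 | 0.185, 0.221 | 0.252, 0.290 | 0.224, 0.255 | 0.269, 0.297 |
| 30%; 25/25 | 0.632, 0.688 | 0.692, 0.743 | 0.653, 0.710 | 0.685, 0.740 |

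The gain of exact stratified over Fisher mixes two things: a less discrete test, and the baseline information. CMH minus unadjusted chi-square isolates the second.

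| Group | Total gain (points) | Baseline's own share (points) |
|---|---|---|
| Strong persistence (rows 1–3) | 7 to 15 | 5 to 12 |
| Rare or weakly prognostic (rows 4–6) | 3 to 4 | 0 to 2 |
| No persistence (row 7) | 2 | −0.7 to −0.3 |

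For example, in row 1 at 80 per arm the total gain is 0.578 − 0.437 = 0.141 and the baseline share is 0.609 − 0.497 = 0.112.

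**Null rejection over all 14 runs.** Fisher 0.008–0.018; exact stratified 0.012–0.022. Both are below 0.025.

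**A second data model.** Let p be the risk of a new event, q the baseline prevalence and r the chance that a baseline symptom recurs. Then the risk of any event is 1 − (1 − qr)(1 − p), and the difference between arms is (1 − qr) times the difference in new-event risk. Assume p is 20% vs 40%, q = 0.4 and r = 0.8. The any-event risks are 1 − 0.68 × 0.80 = 0.456 and 1 − 0.68 × 0.60 = 0.592. The 20-point excess becomes 13.6 points. At 80 per arm, power is 0.24 for Fisher, 0.29 for unadjusted chi-square, 0.43 for CMH and 0.39 for the exact stratified test. With r = 0, Fisher has 0.65, chi-square 0.71 and CMH 0.70, so baseline then adds nothing. The direction agrees with the first model.

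**The case against.** The strongest objection is that nothing here is an error. The window, contrasts, test and threshold are all fixed, Fisher's test holds its level, and an unadjusted participant count is an ordinary choice for a secondary safety outcome. That stands, and it is why the point is an efficiency suggestion only.

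Second, the conditions that decide the size of the loss cannot be seen in the SAP: baseline prevalence, persistence, and whether an unchanged pre-existing symptom is scored as an event. The scoring rule may be in the protocol or in the instrument. If only new or worsened symptoms count, most of the loss disappears. This also stands. It limits the size of the benefit but does not make the change harmful, since the exact stratified test had more power than Fisher in every setting run.

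Third, the event definition may matter more than the choice of test. In the second model at q = 0.4, r = 0.8, Fisher applied to new events only has power 0.65, against 0.39 for the exact stratified test on any event. That is true under that model, but it changes the outcome, whereas stratifying keeps the SAP's outcome as it is.

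Fourth, the SAP has no rule for participants who miss NAEI interviews after baseline. That affects the planned Fisher test and the stratified test alike, so it does not favour either.

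**Conclusion.** The point holds, as something to consider. The planned test is valid but leaves unused a baseline measurement that the trial already collects. The resulting loss of power is conditional: 7–15 points against the exact stratified test if symptoms persist strongly (about 5–12 of them due to baseline itself), 3–4 points if baseline symptoms are rare or weakly prognostic, and about 2 points, all from reduced discreteness, if there is no persistence. These figures assume a conditional odds ratio of 2.5, the tabulated event rates, 80 or 90 per arm and complete interviews. None of the event rates comes from the SAP, so confidence in the size is moderate. The direction held under two different data models whenever symptoms recurred.

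**What to change.** In the Adverse events section, for both contrasts:

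- Make the main test the exact conditional test of any NAEI event at weeks 4–12 by arm, stratified by baseline NAEI status (any event at the baseline visit, yes or no; use the enrollment interview if the baseline one is missing).
- Keep all randomized participants and the 0.025 threshold.
- Report the unadjusted Fisher test as supportive.

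Because the stratified test is exact, it needs no fallback rule for sparse counts. It would also help to say, or to cross-refer to the protocol if it is settled there, whether a symptom present at baseline and unchanged counts as an event.

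The cost is SAP wording and one further test, with no new data, visits or sample size. The stratifier should be nearly complete, because study numbers are "assigned sequentially to eligible participants who enroll in the trial and attend the baseline visit". The downside is slightly more analysis work for only 2–4 points of power if baseline symptoms turn out to be rare, weakly prognostic or not scored as events.
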